#### 4.8.3.3. Dose Adjustments for Subjects of East Asian Ancestry:

The starting dose for patients of East Asian ancestry will be 50mg orally daily. East Asian (i.e. Japanese, Chinese, Taiwanese and Korean) subjects exhibited 50-55% higher eltrombopag plasma concentrations compared to non-East Asian subjects. Dose adjustments for platelet counts will proceed as per 4.8.3.1. regardless of ethnicity.

Dose reductions different than the dose described above are acceptable after discussion with the sponsor and the PI, and will require documentation of the rationale for such action.

#### 4.8.4. Liver Chemistry Stopping and Follow-Up Criteria:

Treatment should be held for any of the following liver chemistry criteria:

1. ALT  $\geq 5x$  ULN and bilirubin  $\geq 2.7x$  ULN ( $>35\%$  direct bilirubin)

2. ALT  $\geq$  8x ULN
3. ALT  $\geq$  5x ULN but  $<$  8x ULN and persists for  $\geq$  2 weeks
4. ALT  $\geq$  5x ULN if associated with the appearance or worsening of symptoms of hepatitis such as nausea, vomiting, right upper quadrant pain or tenderness.
5. ALT  $\geq$  5x ULN but  $<$  8x ULN and cannot be monitored weekly for  $\geq$  2 weeks.

When any of the above criteria is met, do the following:

- Immediately withdraw investigational product

Report the event to Novartis Oncology

- within 24 hours of learning of its occurrence
- Complete the SAE data collection tool if the event also meets the criteria for an SAE. All events of ALT  $\geq$  5x ULN and bilirubin  $\geq$  2.7x ULN ( $>$ 35% direct bilirubin), modified Hy's Law for oncology clinical trials, must be reported as an SAE.

NOTE: if serum bilirubin fractionation is not immediately available, study drug should be discontinued if ALT  $\geq$  5x ULN and bilirubin  $\geq$  2.7x ULN. Serum bilirubin fractionation should be performed if testing is available. If testing is unavailable, record the presence of detectable urinary bilirubin on dipstick, indicating bilirubin elevation and suggesting liver injury.

- Hold eltrombopag until recovery to NCI CTC AE grade 0-1 and restart at next lower dose level regardless of recovery time.

In addition, for #1:

- Make every reasonable attempt to have subjects return to clinic within 24 hours for repeat liver chemistries, liver event follow-up assessments (see below) and close monitoring.
- A specialist or hepatology consultation is recommended.
- Monitor subjects twice weekly until liver chemistries (ALT, AST, alkaline phosphatase, bilirubin) resolve, stabilize or return to within baseline values.

For #2, 3, 4, 5:

- Make every reasonable attempt to have subjects return to clinic within 24-72 hours for repeat liver chemistries and liver event follow-up assessments (see below)
- Monitor subjects weekly until liver chemistries (ALT, AST, alkaline phosphatase, bilirubin) resolve, stabilize or return to within baseline values.

For all Criteria 1-5, make every attempt to carry out the liver event follow-up assessments described below as clinically appropriate:

- Viral hepatitis serology (Hepatitis A IgM antibody; Hepatitis B surface antigen and Hepatitis B core antibody (IgM); Hepatitis C RNA; Cytomegalovirus IgM antibody; Epstein-Barr viral capsid antigen IgM antibody; Hepatitis E IgM antibody if subject resides outside the USA or Canada or has travelled outside the USA or Canada in the past 3 months).
- Serum creatine phosphokinase (CPK) and lactate dehydrogenase (LDH).
- Obtain complete blood count with differential to assess eosinophilia

- Record use of concomitant medications, acetaminophen, herbal remedies, other over the counter medications, or putative hepatotoxins.
- Record alcohol use
- Liver imaging (ultrasound, magnetic resonance, or computerized tomography) to evaluate liver disease.

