### **4.2. Study Duration**

4.2.1. All subjects must complete a screening visit, day 1 visits for each new cycle, an end of treatment visit and whenever possible, an end of study safety visit 28 days after the last dose of eltrombopag.

4.2.2. Treatment will continue until discontinuation due to relapse, unacceptable toxicity, or disease progression as defined by the IWG 2006 criteria for MDS. This includes:

- clinically significant progressive disease at any time, or

- a lack of clinical benefit after 4 cycles of treatment at the highest dose of study medication, or
- Possibility of undergoing allogeneic stem cell transplantation
- discontinuation of study drug for more than 6 weeks, or
- intercurrent illness that prevents further administration of treatment, or
- unacceptable adverse event(s), or
- patient decision for study withdrawal, or
- general or specific changes in the patient's condition that render the patient unacceptable for further treatment in the judgement of the investigator

4.2.3. Study cycles will be administered every 28 days  $\pm$  5 days or upon resolution of any clinically significant study drug related AE to grade 0-1, whichever occurs first. If a subsequent cycle is delayed due to adverse events related to decitabine, or if it is considered in the best interest of the patient to delay administration of decitabine (e.g. because of concern for an infection), administration of the eltrombopag may continue as planned.

4.2.4. Administration of subsequent cycles should be administered when neutrophils recover to  $\geq 1 \times 10^9/L$  and platelets to  $\geq 30 \times 10^9/L$  or to baseline levels prior to the start of the last cycle of therapy. Patients with residual disease may start the next cycle with neutrophil and/or platelet counts lower than these if judged to be in the best interest of the patient to start the next cycle. The decision to treat should be documented in the patient's medical record.

4.2.5. Patients may remain on study for up to 12 cycles if the patient demonstrates clinical benefit and no excessive toxicity (i.e. no clinically significant study-drug related grade  $\geq 3$  toxicity). Patients who are experiencing clinical benefit and have not experienced excessive toxicity may be eligible to continue therapy after discussion with the PI and the discussion documented in the patient's medical record.

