#### 4.8 Dosing Delays and Dose Modifications

##### 4.8.1. Dose Adjustments for Toxicity:

The doses of eltrombopag and decitabine will be adjusted according to the guidelines shown in the following tables for study drug-related clinically significant toxicity. If toxicity is not covered in the table, doses may be reduced or held at the discretion of the investigator for the patient's safety. See section 4.8.4 for liver chemistry stopping and follow-up criteria.

Patients will be withdrawn from the study if they fail to recover to CTCAE grade 0 to 1 (or within 1 grade of starting values for pre-existing laboratory abnormalities) from a clinically significant non-hematologic treatment-related toxicity within 6 weeks (leading to treatment delay of > 4 weeks) unless the investigator feels that the patient should remain in the study because of evidence that the patient is/may continue deriving benefit from continuing study treatment. Such instances will be discussed with the principal investigator on a case by case basis and the discussion documented in the medical record.

Patients with study-drug related toxicities that are manageable with supportive therapy may not require dose reductions. For patients with other drug-related toxicities, the following dose adjustment rules apply:

NCI CTCAE Grade	Action
Grade 0-2 non-hematological toxicity	No dose reduction.  For grade 2 toxicities that are persistent and/or intolerable (e.g. stomatitis) patients may have a treatment interruption or dose

	reductions to the next lower dose level.
Grade 3-4 clinically significant non-hematological toxicity†	Hold until recover to NCI CTC AE grade 0-1  If recovery occurs within 2 weeks after treatment has been held, dose should be reduced to -1 dose level, if applicable.

† see 4.8.4 for additional liver chemistry stopping and follow-up criteria

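### For an eltrombopag liver hold longer than 6 weeks, sections 4.8.4, 4.2.2 and 4.8.1 give three different instructions and none is said to prevail

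*Combined protocol and SAP*

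**What the plan says.** Three sections of the combined protocol and SAP bear on a long liver hold.

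- **Section 4.8.4** lists five liver chemistry criteria. When any is met, the site is told to "Immediately withdraw investigational product" and later to "Hold eltrombopag until recovery to NCI CTC AE grade 0-1 and restart at next lower dose level regardless of recovery time". The restart instruction comes before the text splits into follow-up for criterion 1 and for criteria 2 to 5, so it covers all five. Criterion 1 is the one the protocol calls modified Hy's Law and requires to be reported as an SAE.
- **Section 4.2.2** lists, among the reasons for ending treatment, "discontinuation of study drug for more than 6 weeks". The bullet carries no exception.
- **Section 4.8.1** states: "Patients will be withdrawn from the study if they fail to recover to CTCAE grade 0 to 1", or to within one grade of a pre-existing laboratory abnormality, from a clinically significant treatment-related non-hematologic toxicity within 6 weeks. A parenthesis links this to a treatment delay of more than 4 weeks. The rule applies "unless the investigator feels that the patient should remain in the study because of evidence" of benefit, and adds: "Such instances will be discussed with the principal investigator on a case by case basis", with documentation.

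The 4.8.1 dose table has its own, shorter window for grade 3-4 toxicity: "If recovery occurs within 2 weeks after treatment has been held, dose should be reduced to -1 dose level". Its footnote reads: "see 4.8.4 for additional liver chemistry stopping and follow-up criteria".

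**The concern.** A patient whose liver tests take more than 6 weeks to recover can be handled in three ways, depending on which section the site opens. Section 4.8.4 resumes the drug one level lower, 4.2.2 ends treatment, and 4.8.1 withdraws the patient unless a benefit case has been made and documented.

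The question is re-exposure to a drug that the protocol itself says may cause hepatotoxicity. The background in section 2.3.1 does not recommend reinitiating eltrombopag after its own liver criteria, and allows it only when benefit is considered to outweigh the risk. Section 4.8.1 also has a benefit test. Section 4.8.4 has none, and it covers the modified Hy's Law case. Section 2.3.1 reports that, of seven ITP patients re-exposed after hepatobiliary abnormalities, six had liver test abnormalities again (predominantly Grade 1) and one of these discontinued. That is a different population, and 2.3.1 uses a lower ALT threshold (3 times ULN or baseline, against 5 times ULN or more in 4.8.4). It is support for a documented decision, not evidence of the rate to expect here.

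**Working it through.** The plan gives no figure on this point to reproduce. The check is a comparison of the sections by length of hold.

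**Worked case.** Drug-related ALT reaches 8 times ULN (criterion 2 of 4.8.4), eltrombopag is held, and ALT later recovers to grade 0-1.

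| Length of hold | 4.8.4 | 4.8.1 | 4.2.2 |
|---|---|---|---|
| Up to 2 weeks | Restart one level lower | Table: reduce (read here as one level down) | Not triggered |
| Over 2 and up to 6 weeks | Restart one level lower | Table silent; the withdrawal rule depends on when its clock starts | Not triggered |
| Over 6 weeks | Restart one level lower, no condition | Withdrawn unless a benefit case is discussed and documented | Treatment ends, no exception |

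The first row agrees. The last row conflicts.

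**The middle row and the clock.** Six weeks is 6 × 7 = 42 days, or 42 / 28 = 1.5 cycles. The 4.2.2 limit runs on time off drug. The 4.8.1 limit runs on failure to recover from the toxicity, and its parenthesis about a delay of more than 4 weeks suggests that the two clocks need not start together. Under criterion 3 of 4.8.4, ALT has already been raised for at least 2 weeks before the hold. Six weeks counted from onset could then be as little as 42 − 14 = 28 days of hold. So the 4.8.1 rule might apply before day 42 of the hold. The point is limited to holds longer than 6 weeks, where the conflict does not depend on that choice of start.

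**Does the 4.2.2 bullet cover this hold?** Section 4.8.4 tells the site to withdraw investigational product, and section 4.6 identifies that product as eltrombopag. Treating a long eltrombopag hold as study drug stopped for more than 6 weeks is therefore a natural reading. It is not certain, because 4.2.2 does not define study drug or say whether a temporary hold counts.

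**Size.** The documents give no rate of liver holds over 6 weeks. Expected patients = 40 × assumed rate: 40 × 0 = 0; 40 × 0.025 = 1; 40 × 0.05 = 2. These rates are assumptions only.

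**The case against.** The strongest reply is that the sections can be read in order. Section 4.8.1 decides whether a patient not recovered at 6 weeks stays on study. Anyone still there in week 7 after a clinically significant related toxicity has already passed the benefit discussion, and 4.8.4 then only sets the dose. On this reading, the 4.8.4 phrase about recovery time lifts just the 2-week condition in the 4.8.1 table, whose footnote points to 4.8.4. The opposite reading is also orderly: 4.8.4 is the specific liver rule and overrides the general ones. Both are plausible, but neither is stated. They lead to different actions, the footnote calls the liver criteria additional rather than a replacement, and neither reading removes the 4.2.2 bullet, which has no liver exception.

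A reader might infer that patients would be re-exposed automatically. The documents do not support that. Sections 4.5.2 and 4.8.3.2 leave all eltrombopag dose adjustments to the MD Anderson treating physician. Section 4.2.2 also lets treatment stop for unacceptable adverse events or on the investigator's judgement. Section 4.8.4 requires weekly or twice-weekly liver monitoring and recommends a specialist or hepatology consultation for criterion 1. What stands is that the text permits a restart with no stated benefit test where another section ends treatment.

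It is also fair that the link to 4.2.2 is arguable, since continued decitabine might be said to keep the patient on study drug. That is a second ambiguity, not an answer to the first.

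**Conclusion.** The point holds as a minor but real inconsistency in a patient-safety rule. For an eltrombopag liver hold longer than 6 weeks, 4.8.4 read literally restarts the drug, 4.2.2 ends treatment, 4.8.1 calls for withdrawal or a documented benefit case, and no order of precedence is given. The 4.8.1 part applies only to clinically significant, treatment-related toxicity. The 4.2.2 part assumes that an eltrombopag hold counts as study drug stopped.

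The number of patients affected is unknown and may be zero. A reader might go further and infer bias in the overall response rate, or a problem with the sample size or stopping boundaries. Nothing in the documents supports that: the conflict concerns the handling of individual patients with slow liver recovery, and no effect on the response rate is claimed.

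**What to change.** In 4.8.4, replace the open-ended restart instruction with: *restart one dose level lower, including when recovery takes longer than the 2 weeks in the 4.8.1 table, if the hold has lasted no more than 6 weeks from the first held dose; after a longer hold, restart only if the investigator judges that benefit outweighs the hepatic risk, discussed with the PI and documented as in 4.8.1.*

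In 4.2.2, keep "discontinuation of study drug for more than 6 weeks" and add: *(except an eltrombopag liver hold restarted under 4.8.4)*. The exception should stay this narrow. A general reference to 4.8.1 would loosen the 6-week stop for every toxicity that section covers.

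The sponsor should also confirm that, for liver holds, the clock in the new 4.8.4 wording is the one meant in 4.8.1, so that a clock counted from onset does not withdraw a patient whom 4.8.4 would restart.

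The change needs no extra data, visits or patients. It costs one documented PI discussion for each long liver hold and slightly less freedom to re-challenge. If the authors did intend a restart after any length of hold, they should say so and state that it overrides the other two sections.

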## **2.3. Eltrombopag Safety Profile:**

### **2.3.1 Hepatotoxicity**

Eltrombopag may cause hepatotoxicity. In the controlled clinical trials in chronic ITP, one patient experienced Grade 4 (NCI Common Terminology Criteria for Adverse Events [NCI CTCAE] toxicity scale) elevations in serum liver test values during therapy with eltrombopag, worsening of underlying cardiopulmonary disease, and death. One patient in the placebo group experienced a Grade 4 liver test abnormality. Overall, serum liver test abnormalities (predominantly Grade 2 or less in severity) were reported

in 11% and 7% of the eltrombopag and placebo groups, respectively. In the 3 controlled chronic ITP trials, four patients (1%) treated with eltrombopag and three patients in the placebo group (2%) discontinued treatment due to hepatobiliary laboratory abnormalities. Seven of the patients treated with eltrombopag in the controlled trials with hepatobiliary laboratory abnormalities were re-exposed to eltrombopag in the extension trial. Six of these patients again experienced liver test abnormalities (predominantly Grade 1) resulting in discontinuation of eltrombopag in one patient. In the extension study chronic ITP trial, one additional patient had eltrombopag discontinued due to liver test abnormalities ( $\leq$ Grade 3).

In 2 controlled clinical trials in patients with chronic hepatitis C and thrombocytopenia, ALT or AST  $\geq 3X$  ULN was reported in 34% and 38% of the eltrombopag and placebo groups, respectively. Most patients receiving eltrombopag in combination with peginterferon/ribavirin therapy will experience indirect hyperbilirubinemia. Overall, total bilirubin  $\geq 1.5 X$  ULN was reported in 76% and 50% of patients receiving eltrombopag and placebo, respectively.

Measure serum ALT, AST, and bilirubin prior to initiation of eltrombopag, every 2 weeks during the dose adjustment phase, and monthly following establishment of a stable dose. If bilirubin is elevated, perform fractionation. Evaluate abnormal serum liver tests with repeat testing within 3 to 5 days. If the abnormalities are confirmed, monitor serum liver tests weekly until the abnormality(ies) resolve, stabilize, or return to baseline levels. Discontinue eltrombopag if ALT levels increase to  $\geq 3X$  (ULN) in patients with normal liver function or  $\geq 3X$  baseline in patients with pre-treatment elevations in transaminases and are:

- progressive, or
- persistent for  $\geq 4$  weeks, or

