- accompanied by increased direct bilirubin, or
- accompanied by clinical symptoms of liver injury or evidence for hepatic decompensation.

Reinitiating treatment with eltrombopag is not recommended. If the potential benefit for reinitiating treatment with eltrombopag is considered to outweigh the risk for hepatotoxicity, then cautiously reintroduce eltrombopag and measure serum liver tests weekly during the dose adjustment phase. If liver tests abnormalities persist, worsen or recur, then permanently discontinue eltrombopag.

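### Section 4.8.4 directs eltrombopag to be restarted after any of its five liver criteria, including modified Hy's law and symptomatic ALT rises, without the benefit-risk judgement that 2.3.1 requires

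*Combined protocol and SAP*

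**What the plan says.** Section 4.8.4 (Liver Chemistry Stopping and Follow-Up Criteria) lists five triggers:

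1. ALT at least 5x ULN with bilirubin at least 2.7x ULN, more than 35% direct. The section labels this modified Hy's law.
2. ALT at least 8x ULN.
3. ALT from 5x to below 8x ULN, persisting for 2 weeks or more.
4. ALT at least 5x ULN with new or worsening hepatitis symptoms.
5. ALT from 5x to below 8x ULN when weekly monitoring for 2 weeks or more is not possible.

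A single action list follows for any of the five. It starts with immediate withdrawal of the drug and ends with "Hold eltrombopag until recovery to NCI CTC AE grade 0-1 and restart at next lower dose level regardless of recovery time".

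Section 2.3.1 (Hepatotoxicity) says to discontinue at ALT 3x ULN or more (3x baseline if transaminases were raised before treatment) when one of four conditions is also present: a progressive rise, persistence for 4 weeks or more, increased direct bilirubin, or symptoms of liver injury or decompensation. On rechallenge it says "Reinitiating treatment with eltrombopag is not recommended". The exception is "If the potential benefit for reinitiating treatment with eltrombopag is considered to outweigh the risk for hepatotoxicity, then cautiously reintroduce eltrombopag", with weekly liver tests during dose adjustment, and then "If liver tests abnormalities persist, worsen or recur, then permanently discontinue eltrombopag".

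Two general rules also bear on a long hold. Section 4.2.2 ends treatment for "discontinuation of study drug for more than 6 weeks, or" other listed reasons. Section 4.8.1 withdraws a patient who has not recovered from a clinically significant treatment-related toxicity within 6 weeks, "unless the investigator feels that the patient should remain in the study because of evidence that the patient is/may continue deriving benefit", and asks for a documented discussion with the principal investigator.

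**The concern.** A treating physician with a criterion 1 or criterion 4 event has two instructions. Section 2.3.1 makes stopping the default and asks for a judgement before the drug is given again. Section 4.8.4 makes restart the next step once the grade is 0-1, and no such judgement is mentioned. Two physicians following different sections would treat the same patient differently, and the section with the less cautious instruction is the one in the treatment plan. What is at stake is re-exposure after the most serious liver category the protocol defines. The primary endpoint, the sample size and the stopping boundaries are not involved.

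**Working it through.** The plan gives no figure to reproduce here. The check sets the rules side by side, with a little arithmetic on where they overlap.

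**Step 1: does the restart instruction cover criterion 1?** Yes. It stands in the list common to all five criteria. The measures specific to criterion 1 are introduced as additions to that list, so they do not replace it. They are a return visit within 24 hours, a recommended hepatology consultation and twice-weekly monitoring. None is a condition for restart.

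**Step 2: overlap with 2.3.1 at normal baseline liver function.** The ALT threshold in 2.3.1 is then 3x ULN. The thresholds in 4.8.4 are 5x or 8x ULN, so all five criteria pass the ALT part. What remains is the accompanying condition.

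| 4.8.4 criterion | Accompanying condition in 2.3.1 | Result |
|---|---|---|
| 1 | Increased direct bilirubin | Contradiction whenever direct bilirubin is increased |
| 4 | Symptoms of liver injury | Direct contradiction |
| 2, 3, 5 | None built in | Contradiction only if the rise is also progressive, lasts 4 weeks or more, or comes with raised direct bilirubin or symptoms |

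None of these depends on slow recovery. They arise even if ALT returns to grade 0-1 within days.

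**Step 3: does criterion 1 always mean increased direct bilirubin?** More than 35% of at least 2.7x ULN gives direct bilirubin above 0.35 × 2.7 = 0.945 times the ULN for total bilirubin. Whether that counts as increased depends on the laboratory's upper limit for direct bilirubin, which the documents do not give. If that limit is at or below 0.945 of the total-bilirubin ULN, every fractionated criterion 1 event qualifies. If it is higher, some events at the edge of the criterion may not. The claim is therefore kept conditional.

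**Step 4: raised baseline ALT.** With baseline b (in multiples of ULN) the 2.3.1 threshold is 3b. An ALT of 5x ULN is certain to reach it only if 3b ≤ 5, that is b ≤ 5/3 = 1.67. At an assumed b = 2 the threshold is 6x ULN. At b = 3, the ALT bound in inclusion criterion 6, it is 9x ULN, so an event from 5x to below 9x would not meet 2.3.1.

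**Step 5: the 6-week limits.** If recovery comes within 6 weeks, nothing in 4.2.2 or the 4.8.1 withdrawal rule is breached. Beyond 6 weeks, 4.8.4 read literally says restart, 4.2.2 says treatment has ended, and 4.8.1 says withdraw unless its benefit exception is used.

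**Step 6: internal wording of 4.8.4.** For the same events the section uses *withdraw*, *hold* and *restart*. For ALT at least 5x with bilirubin at least 2.7x ULN, when fractionation is not immediately available, its note says the drug should be *discontinued*. It does not say how these fit together.

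**Context on re-exposure.** Section 2.3.1 reports seven ITP patients re-exposed after liver abnormalities: "Six of these patients again experienced liver test abnormalities (predominantly Grade 1) resulting in discontinuation of eltrombopag in one patient". That is 6/7 = 86% (exact 95% CI 42% to 99.6%) with recurrence and 1/7 = 14% (0.4% to 58%) stopping the drug.

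**The case against.** The strongest reply concerns the recovery-time phrase. The 4.8.1 table prescribes a one-level reduction only "If recovery occurs within 2 weeks after treatment has been held". Section 4.8.4 may simply fill that gap: the same reduction applies however long recovery takes. On that reading it sets the restart dose and leaves the 6-week limits in force. This stands. A reader might infer that 4.8.4 flatly contradicts 4.2.2 and 4.8.1. The documents support that only if recovery takes more than 6 weeks and the phrase is also read as overriding the limits.

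Second, 4.8.4 may be meant as the specific rule, since 4.8.1 points to it twice and 2.3.1 sits in the background section. That is plausible but unstated. The 4.8.1 footnote calls the 4.8.4 criteria additional, and 2.3.1 is worded as instructions. If 4.8.4 does govern, restart after modified Hy's law still has no stated benefit-risk test.

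Third, a reader might see an unavoidable order to rechallenge. The text does not go that far. The same list also says to withdraw, eltrombopag dose decisions belong to the MD Anderson treating physician, 4.2.2 allows stopping for unacceptable adverse events or on investigator judgement, criterion 1 must be reported as an SAE, and chemistries are weekly for 4 weeks after a dose change (4.8.3.2). These safeguards lower the risk. They do not say which rule applies or what test precedes restart.

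**Conclusion.** The concern holds in a limited form. As written, 4.8.4 directs restart one dose level lower after all five liver criteria with no benefit-risk test. At normal baseline liver function this contradicts 2.3.1 outright for criterion 4, for criterion 1 when direct bilirubin is increased, and conditionally for criteria 2, 3 and 5. With raised baseline ALT, an ALT of 5x ULN is certain to reach the 2.3.1 threshold only up to a baseline of 1.67x ULN. The conflict with the 6-week limits is secondary and depends on slow recovery and on how one phrase is read.

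The number of patients affected is unknown and may be zero of 40: the documents give no rate of these liver events or of late recovery. The 6 of 7 re-exposure figure might tempt a reader to expect Hy's law to recur. It does not support that. The patients had ITP, the recurrences were predominantly grade 1, and none is described as Hy's law. Nor is there an argument from dose, since section 2.2 reports no increase in liver-enzyme events at higher doses. No statistical result changes. This is a patient-safety clarification that should be made because it is specific and cheap.

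**What to change.** Replace the restart bullet in 4.8.4 with:

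> Hold eltrombopag until recovery to grade 0-1. After criterion 1 or 4, or any event meeting a discontinuation criterion in 2.3.1, discontinue; restart is not recommended and may occur only if benefit is judged to outweigh the hepatotoxicity risk, after documented discussion with the principal investigator. After other events, restart at the next lower dose level. All restarts are subject to the 6-week limits in 4.2.2 and 4.8.1. After any restart, measure liver tests weekly during dose adjustment and discontinue permanently if abnormalities persist, worsen or recur.

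Leave 4.2.2 unchanged; nothing here requires it to be loosened. With this text, withdrawal in the first bullet reads as the immediate stop, and the new bullet says what follows.

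The cost is a wording amendment in one place and little extra testing, because weekly chemistries for 4 weeks after a dose change are already required. The downside is that a few patients with these events, including some who recover quickly, would stop eltrombopag instead of restarting automatically. For criteria 1 and 4 in patients with raised baseline ALT, the new rule is stricter than 2.3.1 alone, and the sponsor should adopt it knowingly.
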